12.4.2. Analysis Plan

Approximately 60% of SABR patients develop acute radiologic changes in the lung at 3 months [16]. Late radiologic changes, reflecting fibrosis, are more frequent in SABR patients at 1 year [15]. Our institutional experience revealed the presence of moderate-to-severe late radiation induced fibrosis in ~75% of patients treated with SABR (50 Gy in 4 fractions) via VMAT technique at 1 year.

Primary analysis: The outcome of moderate-to-severe radiologic fibrosis rate will be tested in evaluable patients in a one-sample one-sided test of proportion comparing the observed rate, which is expected to be at most 58%, to the historically observed rate of ~75%. The observed rate and the 95% confidence interval calculated using the exact method will be reported.

Secondary analysis: Local control at 12 months will be estimated along with a one-sided lower 95% confidence bound to allow an informal assessment of the null hypothesis that the proportion is larger than 80%. Patients with distant progression before local failure will be censored one day after the last imaging study; patients who die before local control will be censored at the time of death. These definitions are used for comparability. Cumulative incidence estimates for local failure and other failure type will also be presented.

Time to event data (local control, PFS, time to progression) will be evaluated using Kaplan-Meier estimates with 95% confidence intervals at multiples of 12 months based on Greenwood's formula with a log transform. Confidence intervals for median times to event, if relevant, will be constructed using the method of Brookmeyer and Crowley.

Proportions (eg, proportion of patients with grade 4 or higher toxicity) will be estimated along with 95% exact confidence intervals. Patient clinical and demographic characteristics will be reported with the appropriate summary statistic (mean, range, proportion, etc.) Adverse events will be tabulated by organ system and severity.

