12.5 Sample Size

12.5.1 Accrual Estimates

Number of Patients: 55 to 60

In 2014, ~80 lung SABR procedures were performed at Stanford Hospital. It is estimated that 2 to 3 patients can reasonably be expected to accrue per month. Accrual will occur over 60 months.

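### Section 12.4.2 states the 80% local control null in the direction that its one-sided lower bound can never reject

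*Combined protocol and SAP*

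**What the plan says.** For 12-month local control, the secondary analysis paragraph of section 12.4.2 reports the estimate together with this: "one-sided lower 95% confidence bound to allow an informal assessment of the null hypothesis that the proportion is larger than 80" per cent. It gives no alternative hypothesis, upper bound or decision rule for this benchmark, and no other section restates the null.

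Two interval methods appear in the same section. Local control is named among the time-to-event outcomes: "Time to event data (local control, PFS, time to progression) will be evaluated using Kaplan-Meier estimates with 95% confidence intervals". Those intervals use the Greenwood variance on the log scale and are read at yearly time points. A later sentence gives proportions exact 95% intervals, and the local control sentence itself calls the quantity a proportion. The section does not say which method produces the one-sided bound.

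There is no sample size or power statement for local control. Section 12.5.2 sizes phase 2 at 50 for fibrosis. Section 12.5.1 gives the total: "Number of Patients: 55 to 60".

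**The concern.** A null hypothesis is the statement that the data may contradict. Here the null is the favourable outcome (control above 80%), and the tool paired with it can contradict only unfavourable values. The plan appears to have written the alternative where the null belongs.

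What is at stake is the conclusion drawn from the plan's only numerical benchmark for local control. Taken literally, the report will always say that the null was not rejected. Next to a null of more than 80%, that sentence could be taken as support for preserved control when it was certain before any patient was enrolled.

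**Working it through.** **Inputs.** One-sided 95% lower bound, 80% benchmark, and the Greenwood log-transform and exact methods: section 12.4.2. n = 50: section 12.5.2. n = 55 and 60: section 12.5.1. The plan does not say which of these denominators applies to local control, so all three are shown. The illustrations assume that every patient's 12-month local status is known (no censoring). The plan states no figure for local control that could be reproduced.

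**Step 1, direction.** A one-sided lower bound L gives the confidence set [L, 100%] and excludes only values below L.

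- Null of more than 80%: rejection requires every value above 80% to lie outside [L, 100%]. The set always reaches 100%, so this cannot happen.
- Null of 80% or lower: rejection requires L > 80%, which can happen.

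This holds for any estimator, with or without censoring. At n = 50, exact bounds: 0/50 gives L = 0 and 50/50 gives L = 94.2%. Neither rejects a null of more than 80%.

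**Step 2, a poor result.** Take 30/50 controlled, S = 0.60. Without censoring, the Greenwood variance of log S is (1 − S)/(nS), so the bounds are S·exp(∓1.645·√[(1 − S)/(nS)]).

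- √(0.40/30) = 0.1155, and 1.645 × 0.1155 = 0.190.
- Lower: 0.60 × exp(−0.190) = 49.6%. The stated null is not rejected.
- Upper: 0.60 × exp(+0.190) = 72.5%. An upper bound would have rejected it.
- The exact method agrees: lower 47.4%, upper 71.7%.

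**Step 3, the bound with the null turned round.** With the null at 80% or lower, find the smallest count x for which L > 80%. The log-transform bound is as in step 2. The exact bound is the 5th percentile of Beta(x, n − x + 1). The last column is P(X ≥ x) for X ~ Binomial(n, 0.80), the probability of reaching that count when true control is exactly 80%.

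| n | Method | One fewer: L | First count with L > 80%: L | P at true 80% |
|---|---|---|---|---|
| 50 | log transform | 43/50: 78.3% | 44/50: 80.8% | 0.103 |
| 50 | exact | 44/50: 77.7% | 45/50: 80.1% | 0.048 |
| 55 | log transform | 47/55: 78.0% | 48/55: 80.2% | 0.116 |
| 55 | exact | 49/55: 79.6% | 50/55: 81.8% | 0.025 |
| 60 | log transform | 52/60: 79.7% | 53/60: 81.8% | 0.067 |
| 60 | exact | 53/60: 79.2% | 54/60: 81.2% | 0.031 |

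For example, 44/50 by log transform: 0.88 × exp(−1.645 × √(0.12/44)) = 0.88 × exp(−0.0859) = 80.8%.

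**Step 4, reading the table.** The cut-off depends on the method, by one patient at n = 50 and 60 and by two at n = 55. Without censoring, the log-transform cut-offs are reached more often than the nominal 5% when true control is 80%: about twice as often at n = 50 and 55. The exact cut-offs stay below 5%. This is why the method should be named along with the corrected null.

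**The case against.** The strongest reply is that this is a wording slip with a recoverable meaning. A lower bound set against 80% has one sensible purpose, to show that control exceeds 80%. Section 2.2 cites 98% local control at 3 years after SABR, which fits that purpose. A statistician would compute the same bound and compare it with 80%. The assessment is labelled informal, no sample size or go/no-go rule depends on it, and the rules in section 7.12 use toxicity, recurrence counts and new malignancies instead. All of this stands and keeps the point small. It does not make the sentence correct: a prespecified hypothesis should not need the reader to reverse it.

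Three stronger readings are tempting, and the documents do not support them.

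- A reader might infer that poor local control could go unseen. It could not. In the 30/50 example the report would show a 60% estimate and a lower bound near 50%, and section 12.4.2 also plans a two-sided Kaplan-Meier interval and the cumulative incidence of local failure.
- A reader might infer that the log-transform method is settled for this bound, making 44/50 the cut-off. The Greenwood sentence covers the 95% intervals for time-to-event data, while the local control sentence speaks of a proportion, and proportions get exact intervals.
- A reader might infer that the plan meant to detect control below 80% and chose the wrong bound. That would be coherent with an upper bound, but nothing in the documents points to it.

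**Conclusion.** Wrong as written, with minor consequence. The mismatch between null and bound is a matter of logic and rests on no assumption about censoring, denominator or estimator. Its effect is confined to the interpretation of one secondary, informal benchmark: the stated null can never be rejected, so its survival carries no information about preserved control. The estimate, the lower bound under whichever method is used, the primary fibrosis test and the sample of 50 do not change.

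The cut-offs in the table are illustrations only. They assume no censoring, whereas section 12.4.2 censors local control at distant progression and at death, so they will not carry over directly to the Kaplan-Meier analysis.

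**What to change.** In the secondary analysis paragraph of section 12.4.2:

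1. Restate the null as 12-month local control of 80% or lower, keep the assessment informal, and add that control above 80% is supported if the one-sided lower 95% bound exceeds 80%.
2. State which method gives that bound: Kaplan-Meier with Greenwood variance and log transform, or exact binomial. If exact, also say how patients censored before 12 months are counted.
3. If illustrative cut-offs are added, show them under both methods with their probabilities at true control of 80% and the no-censoring assumption.

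The cost is one clause and one sentence on method. No data, sample size or patient procedure changes.

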4.2.3 Duration of Therapy

Patients will be seen on Days 1, 15, and 36 when they receive fresolimumab, and will be seen in follow-up at 3rd; 6th; 9th and 12th month from end of SABR completion (+/- 2 weeks). History and physical exam, ECOG PS, toxicity evaluation, CT Thorax (Chest) imaging, and labs will be evaluated at each of these visits. Skin exams will be conducted at the 3rd month from end of SABR completion. PFTs will be completed at 6th and 12th month. PET/CT imaging will be evaluated at 6th month. The duration of the treatment phase of the study will be through the 1st follow-up visit, approximately 90 days after the SABR is completed.

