9. STUDY CALENDAR

Parameters	Pre-Entry ⁶	Day 1	Day 8-12 ⁴	Day 15 ⁷	Day 36 ⁸	3 month ^{9,10}	6 month ¹⁰	9 month ¹⁰	12 month ¹⁰
History & Physical Exam	X	X		X	X	X	X	X	X
Complete skin exam ¹	X					X			
ECOG PS	X	X		X	X	X	X	X	X
Labs ²	X	X		X	X	X	X	X	X
CT Thorax (Chest)	X ¹¹					X	X	X	X
PET/CT	X ¹¹						X		
Toxicity evaluation		X		X	X	X	X	X	X
PFT ³	X						X		X
SABR ⁴			X						
Fresolimumab ⁵		X		X	X				

- ¹ To be performed by the investigators. Suspect lesions will be referred for further evaluation to a dermatologic oncologist or dermatologist as appropriate
- ² Includes CBC with differential and complete metabolic panel. Also urine or serum pregnancy test required for women of childbearing potential at pre-entry only
- ³ Including DLCO, FEV1, and FVC
- ⁴ 12.5 Gy/fraction in 4 fractions between Days 8 to 12. Minus 1 to + up to 5 days to allow for weekends and holidays and unforeseen circumstances.
- ⁵ 3 mg/kg IV (or other determined dose from Phase 1) given on days 1, 15, and 36
- ⁶ All pre-entry assessment should be obtained within 4 weeks of enrollment
- ⁷ 3 days after completion of SABR, + up to 6 more days to allow for weekends and holidays and unforeseen circumstances
- ⁸ Target 21 days after dose 2 of fresolimumab. +/- 6 days to allow for weekends and holidays and unforeseen circumstances
- ⁹ Needs to be at least 90 days after completion of SABR for safety analysis
- ¹⁰ +/- 2 weeks to allow for weekends and holidays and unforeseen circumstances. Date counted from completion of SABR.
- ¹¹ Acceptable to use non-diagnostic simulation planning scans for baseline imaging

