Hilar node failure (HNF)	Appearance of tumor in ipsilateral hilar lymph nodes.
Ipsilateral mediastinal nodal failure (MNF)	Appearance of tumor in ipsilateral mediastinal and/or subcarinal lymph nodes.
Distant Failure	
Distant nodal failure (DNF)	Appearance of tumor in ipsilateral supraclavicular or contralateral lymph nodes.
Distant metastatic failure (DMF)	Appearance of tumor deposits characteristic of NSCLC metastasis (chest wall other than incision sites or immediately adjacent to primary, mediastinal structures/diaphragm, malignant pleural effusion/pericardial effusion), contralateral lung and/or other distant sites.

Potential adverse events will be monitored by treating physicians at each follow-up visit, and scored using CTCAE v4 with type and grade.

Post-treatment changes in pulmonary function will be evaluated by changes in pulmonary function test at enrollment, 6-month, and 12-month follow-up.

Recurrence rate is determined by time from study enrollment to first documented date of recurrence.

Progression-free survival (PFS) is time from time from study enrollment until the first documented date of disease progression.

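### Kaplan-Meier at 12 months from enrollment leaves out most failures first found on the last scheduled scan, so 12-month local control and PFS are modestly overstated

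*Combined protocol and SAP*

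**What the plan says.** Section 12.4.2 (secondary analysis) specifies "Kaplan-Meier estimates with 95% confidence intervals at multiples of 12 months" for local control, PFS and time to progression. For local control it adds: "Local control at 12 months will be estimated along with a one-sided lower 95% confidence bound". That bound is set informally against 80%.

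Section 10.2 fixes the clock. "Recurrence rate is determined by time from study enrollment to first documented date of recurrence", and PFS "is time from time from study enrollment until the first documented date of disease progression". Local control is given no time zero of its own, so the recurrence definition is the nearest stated rule.

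The scans run on another clock. Section 4.2.3 and the Study Calendar (Section 9, footnote 10) place visits at 3, 6, 9 and 12 months, plus or minus two weeks: "Date counted from completion of SABR". SABR itself is "12.5 Gy/fraction in 4 fractions between Days 8 to 12", with an allowance of minus one to plus five days. The 12-month CT is the last scheduled scan.

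Sections 4.2.4 and 10.1 count 12 months from enrollment instead, which conflicts with Sections 4.2.3 and 9. No section assigns scan findings to nominal visits or calls for an interval-censored method.

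**The concern.** A failure is normally documented on a scan. If the last scan usually happens after the time at which the curve is read, failures first seen on that scan count as events after the landmark. The figure labelled 12 months then reflects little beyond the 9-month scan.

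The error runs in the favourable direction. In a single-arm trial there is no concurrent control arm to share it. Section 12.4 names recurrence and PFS at 12 months as endpoints, and Section 12.4.2 sets local control against a fixed 80%, so the reported value is likely to be read at face value.

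**Working it through.** **No plan figure to reproduce.** The documents give no precision or expected rate for 12-month local control or PFS. The Phase 2 sample size of 50 concerns fibrosis; here it only sets the number of patients.

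**Inputs from the documents.** Clock from enrollment to first documentation (10.2); curve read at 12 months (12.4.2); last scan 12 months after SABR completion, ±14 days (4.2.3, 9). SABR on Days 8 to 12, −1/+5 days, with the second fresolimumab dose (Day 15) timed 3 days after SABR completion (9), gives completion on about Day 12, Day 17 at the latest.

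**Assumptions.** 12 months = 365 days; enrollment on Day 1 (the gap is not stated, and zero is most favourable to the plan); earliest SABR completion Day 10; scans uniform over the 29 permitted days; constant hazard; failures dated on the scan; failure-free patients censored at their last scan; no deaths or losses.

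**Step 1: how many 12-month scans are late.** Let k be the days from enrollment to SABR completion. The scan falls on day 365 + k + d, with d from −14 to +14, and is late when d > −k. The late share is (k + 14)/29, capped at 1.
- SABR ends Day 10 (k = 9): 23/29 = 79%.
- Day 12 (k = 11): scan on days 362 to 390; 25/29 = 86%.
- Day 17 (k = 16): 100%.
- Equal weight on Days 10 to 17: (23+24+25+26+27+28+29+29)/(8 × 29) = 211/232 = 91%.
- SABR ends Day 12 and enrollment precedes Day 1 by four days or more (k ≥ 15): 100%.
- Scans and endpoints on one origin (k = 0): 14/29 = 48%.

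**Step 2: size by hand.** If no 12-month scan counted, the curve at day 365 would reflect failures up to the 9-month scan, about day 274 + 11 = 285. A true 12-month rate S would read as S^(285/365). This is roughly the upper limit.

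**Step 3: size by simulation** (trials of 50 patients, SABR ending Day 12 or spread over Days 10 to 17).

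| True 12-month rate | S^(285/365) | Kaplan-Meier at day 365 | Events and censoring dated to nominal visit |
|---|---|---|---|
| 70% | 75.7% | 75.0–75.4% | 69.3–69.4% |
| 80% | 84.0% | 83.2–83.7% | 79.3–79.5% |
| 90% | 92.1% | 91.7–91.9% | 89.7% |
| 95% | 96.1% | 96.0% | 94.9% |
| 98% | 98.4% | 98.4% | not run |

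With SABR ending Day 12, 20% to 24% of all observed failures were found on the 12-month scan, and about 88% of those were dated after day 365. Visit-dated values sit slightly below the truth because that scan falls on average a little after day 365.

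**Step 4: the bound against 80%.** At a true 80%, the one-sided lower 95% bound exceeds 80% in about 25% to 27% of trials, against about 9% to 10% with visit-based dating. The comparator is not 5% because the log-transformed bound clears 80% with 6 failures in 50 (0.88 × exp(−1.645 × √(0.12/(0.88 × 50))) = 0.808) but not with 7 (0.783), and P(6 or fewer of 50 at 20%) = 0.103.

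**Step 5: one shared origin.** With 48% of scans late, a true 80% reads as about 82%. Aligning the clocks removes about half of the bias, not all of it.

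**The case against.** The strongest reply is that the effect is small and governs nothing. Much of that stands. At a true 80% the bias of 3 to 4 points is below one standard error, √(0.8 × 0.2/50) = 5.7 points. Section 2.2 cites 98% local control at 3 years after SABR; near that level the bias is under half a point, and at a true 95% the bound clears 80% in about 99% of trials under either dating. The 25% to 27% figure belongs to a true rate of exactly 80%.

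It can also be said that no section writes day 365, that the calendar uses 12 months as a visit label, and that the synopsis defines recurrence as present or absent by 12 months. A simple proportion built on that definition would naturally include the 12-month visit. But the Kaplan-Meier analysis needs dates, and the dates in Section 10.2 place most of these failures after the landmark. If the visit is meant, the plan has to say so.

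The word "most" depends on the anchor. If scans followed the enrollment anchor of Sections 4.2.4 and 10.1, or local control were timed from SABR completion, it would be about half.

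A reader might infer that recurrence safety monitoring is compromised. The documents do not support that. Section 7.12 pauses enrollment at three or more recurrences in the first 10 subjects through 6 months, and does not use the 12-month curve. Nor is the 80% comparison a decision test; Section 12.4.2 calls it informal.

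**Conclusion.** The point holds for the Kaplan-Meier readings at 12 months. It follows from rules the plan states: an enrollment clock, first-documentation dating, and a last scan counted from SABR completion. With enrollment on Day 1 and SABR ending Day 10 to 17, roughly 80% to 100% of the last scans fall after the landmark. The overstatement is about 5 points at a true 70%, 3 to 4 at 80%, 2 at 90%, 1 at 95% and under 0.5 at 98%.

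The direction does not depend on the assumed rates; the size does, together with the constant hazard and uniform scan timing. Confirmation by biopsy or by a change in management (Section 10.2) can only delay the documented date. The consequence is confined to secondary endpoints and one informal comparison. The primary fibrosis test, the sample size and the Section 7.12 pause rule are unaffected.

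**What to change.** In Section 12.4.2:
- State one time origin for scans and endpoints, and reconcile Sections 4.2.4, 10.1 and 10.2 with Sections 4.2.3 and 9.
- For local control, PFS, time to progression and the cumulative incidence curves, assign both scan-detected events and scan-based censoring to the nominal 3-, 6-, 9- or 12-month visit, so that the 12-month estimate includes failures found at that visit. An interval-censored estimate would also serve.
- Keep the actual-date analysis as a sensitivity analysis.

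Moving the reading point to the end of the 12-month window is not a substitute. Failure-free patients are censored on their own scan day, so the risk set collapses across the window: a true 80% then reads as about 64% to 67%, and a true 90% as about 83%.

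The cost is wording only, with no new scans or patients. The reported 12-month rates become slightly less favourable.

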2.2 Study Agent/Device/Procedure

Stereotactic Ablative Radiotherapy

In non-operable NSCLC patients, stereotactic ablative radiotherapy (SABR), also called stereotactic body radiation therapy (SBRT), has recently emerged as an important treatment option [3, 4]. A landmark prospective phase 2 clinical trial conducted by the Radiation Therapy Oncology Group, RTOG 0236, found that SABR resulted in outstanding local control (LC) and overall survival (OS) rates of 98% and 56% at 3 years in a cohort of strictly medically inoperable patients with peripherally located stage I NSCLC [5]. While extremely well tolerated, SABR almost always produces a significant fibrotic reaction in the targeted region of the lung. These fibrotic reactions result in loss of function of the affected lung tissue and significantly complicate detection of post-SABR recurrences.

Transforming growth factor-beta

Transforming growth factor-beta (TGF β) is a pleiotropic cytokine expressed as three isoforms; TGF β 1, TGF β 2, and TGF β 3 and belongs to a superfamily of ligands comprised of more than 30 proteins such as bone morphogenetic proteins, activins, and inhibin. TGF β isoforms are involved in a number of normal biologic and physiologic processes such as cell proliferation, cell differentiation, cell motility, apoptosis, angiogenesis, and extracellular matrix production [6]. In normal non-cancerous cells TGF β limits the growth of epithelial, endothelial, neuronal, and

hematopoietic cells through induction of anti-proliferative and apoptotic responses but in cancer TGF β has been shown to have growth promoting and prometastatic effects [7, 8].

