12.5.2 Sample Size Justification

Phase 1:

Post-SABR pneumonitis grade 3 or greater is expected to occur in $\leq 10\%$ of patients with stage I disease. Based on this percentage, we propose to start out with a cohort of 5 patients at the pre-selected dose of 3 mg/kg of fresolimumab. If one patient develops DLT, then 5 more patients will be enrolled at the same dose to make a total of 10 patients. If no more patients

experience DLT, then the total percentage of patients experiencing DLT is 10% and is considered acceptable for toxicity.

Phase 2:

A sample of size 50 was chosen in order to have 80% power to detect a decrease in the incidence of post-SABR moderate-to-severe fibrosis from 75% to 60% with a one-sided significance level of 10%.

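### The planned Greenwood limits with a log transform give too high a lower bound for 12-month local control, and with no local failures they give no bound at all

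*Combined protocol and SAP*

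**What the plan says.** All the relevant text is in section 12.4.2 (Analysis Plan).

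- The secondary analysis opens with "Local control at 12 months will be estimated along with a one-sided lower 95% confidence bound". The stated purpose is "to allow an informal assessment of the null hypothesis that the proportion is larger than 80" percent. The sentence names no method for the bound.
- Censoring rules follow. For distant progression: "Patients with distant progression before local failure will be censored one day after the last imaging study". Deaths are also censored, at the date of death.
- The next paragraph says "Time to event data (local control, PFS, time to progression) will be evaluated using Kaplan-Meier estimates", and specifies the method in full as "Kaplan-Meier estimates with 95% confidence intervals at multiples of 12 months based on Greenwood's formula with a log transform". Local control is listed first.
- A later paragraph says that proportions "will be estimated along with 95% exact confidence intervals".

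The section does not say whether the log transform is log(S) or log(-log S), and it gives no rule for the case of no failures.

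**The concern.** Local control is given censoring rules and is listed by name among the Kaplan-Meier endpoints. Greenwood with a log transform is therefore the natural method for its one-sided bound. That method behaves poorly when the estimate is close to 100% and the sample is about 50. The error is in the reassuring direction: the lower limit is too high. A reader could be told that control is above 80% with 95% confidence when the data do not support that level, or be shown a limit of 100% from about 50 patients.

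Few failures are plausible here. Section 2.2 cites a SABR series with "outstanding local control (LC) and overall survival (OS) rates of 98% and 56% at 3 years".

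**Working it through.** **Inputs.** Section 12.5.2 gives n = 50: "A sample of size 50 was chosen in order to have 80% power to detect a decrease in the incidence" (75% to 60%, one-sided 10%). That figure is consistent: a one-sample normal approximation with continuity correction gives 48.0, so 49, and the exact rule at n = 50 (33 or fewer cases) has error 9.8% and power 84.4%. The plan states no error rate for the local control bound beyond its nominal 5%, so there is no figure of its own to reproduce there. The number analyzed is uncertain: section 12.5.1 gives 55 to 60 patients in all, and section 12.4.1 restricts analysis to completers with further exclusions. I therefore also take n = 46 to 60 as an assumption.

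**Formulas.** Without censoring, the 12-month Kaplan-Meier estimate is S = x/n for x patients controlled, and the Greenwood standard error of log S is se = sqrt((1 - S)/(nS)). One-sided 95% lower bounds:
- log(S): S × exp(-1.645 × se)
- log(-log S): S^exp(1.645 × se/|ln S|)
- exact (Clopper-Pearson): 5th percentile of Beta(x, n - x + 1)

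**Worked case, 6 failures in 50.** S = 0.88 and se = sqrt(0.12/44) = 0.0522.
- log(S): 0.88 × exp(-0.0859) = 0.808
- log(-log S): |ln 0.88| = 0.1278, exponent exp(0.672) = 1.958, and 0.88^1.958 = 0.779
- exact: 0.777

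**Other counts, n = 50.**

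| Failures | log(S) | log(-log S) | Exact |
|---|---|---|---|
| 0 | 100% | 100% | 94.2% |
| 1 | 94.8% | 90.1% | 90.9% |
| 2 | 91.6% | 87.8% | 87.9% |
| 3 | 88.6% | 85.2% | 85.2% |
| 5 | 83.3% | 80.3% | 80.1% |
| 6 | 80.8% | 77.9% | 77.7% |
| 7 | 78.3% | 75.5% | 75.3% |

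**Error at true control 80%.** The log(S) bound exceeds 80% with 6 or fewer failures: P(X ≥ 44 | 50, 0.80) = 10.3%. The log(-log S) and exact bounds need 5 or fewer: P(X ≥ 45) = 4.8%. Over n = 46 to 60 the log(S) error runs from 6.2% (n = 48) to 11.6% (n = 49 and 55). It is 6.7% at n = 60. In simulation with three-monthly scans and an assumed 10% to 30% censored by 12 months, the log(S) error is about 8% to 10%. With 0% to 30% censored, the log(-log S) error is about 2.4% to 4.6%.

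**Where the error comes from.** At n = 50 and true control 80%, the two-sided 95% log(S) interval covers 94.6%, but it misses 4.8% of the time with the lower limit too high and 0.6% with the upper limit too low. Total coverage is about right; the split between the tails is not, and a one-sided lower bound uses the bad tail.

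**Zero failures.** With S = 1, se = 0 under any transform and the bound is 100%. The exact bound is 0.05^(1/50) = 94.2%. The probability of this outcome is 0.95^50 = 7.7% at true control 95% and 0.98^50 = 36.4% at 98%.

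**Does the proposed change work?** With log(-log S) plus the exact bound at zero failures, the error at n = 50 is 4.8% at true control 80%, 3.4% at 90%, 4.5% at 94% and 0 at 95% and 98%.

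**The case against.** Several points on the other side are fair.

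- *The transform is ambiguous.* The text does not say plain log. If log(-log S) was meant, the error at 80% with n = 50 is 4.8% and the 10.3% figure disappears. This stands as a limit on the first half of the point. The zero-failure half is unaffected.
- *The one-sided sentence names no method.* It calls the quantity a proportion, and proportions get exact intervals elsewhere in the section. An exact bound would also give 4.8%. But a simple exact binomial interval does not accommodate the censoring that the section prescribes for this endpoint, so Kaplan-Meier with Greenwood remains the more natural reading.
- *The size depends on n.* At n = 50 the whole difference is one patient, 44 controlled against 45.
- *The analysis is informal.* No go/no-go decision, stopping rule or sample size rests on it. Early recurrence has its own enrollment-pause trigger in section 7.12. When control is near 98% the bound clears 80% by any method (with one failure, 94.8% or 90.9%), so what suffers is the reported limit, not the reading against 80%.

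A reader might infer more than the documents support. One inference is that the interval is far too narrow and that this causes the 10% error. At 80% the two-sided coverage is 94.6%, so the cause is unequal tails. Another is that the log transform causes the 36% error at 98% control. That figure is simply the chance of no failures, and log(-log S) shares it exactly. A third is that the protocol expects 98% control in this trial. The 98% is background from a peripheral stage I series, whereas this trial admits tumors up to T2b and 5 cm and states no expected rate.

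**Conclusion.** The point holds, in two separate parts.

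1. If the log transform is log(S) and it supplies the one-sided bound, the nominal 5% error at true control 80% is 10.3% with 50 patients and no censoring, and about 6% to 12% over 46 to 60 patients. With one to six failures in 50 the reported limit is about 3 to 4 points above the exact one.
2. If Greenwood's formula supplies the bound under any transform, a trial with no local failures reports a limit of 100% in place of 94.2%. At n = 50 this has probability 7.7% if true control is 95% and 36% if it is 98%. Both rates are illustrations, not planning values.

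It would be going too far to say that the plan's conclusions on efficacy are at risk, or that this must be settled before the trial can be interpreted. The analysis is secondary and labeled informal, and the primary fibrosis test and its sample size are untouched. It should be fixed because the specified limits are wrong in the reassuring direction and better ones are readily available.

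**What to change.** In section 12.4.2:

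1. Specify the complementary log-log transform of the Kaplan-Meier estimate for local control, PFS and time to progression.
2. State that the one-sided lower 95% bound for 12-month local control uses the same method.
3. State that when local failures are zero or very few, the bound is of exact type: beta-product with censoring, Clopper-Pearson without. Give the failure count at which the switch applies. Changing the transform alone does not cure the zero-failure case, so this third item is needed.

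The cost is two or three sentences and no new data. The only downside is a somewhat lower reported limit, about 3 to 6 points at n = 50 for zero to six failures. At n = 50, 5 failures would still clear 80% (80.3%) and 6 would not (77.9%), in line with the exact bound.
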